7. RESEARCH MONITORING

Study will be monitored by Faculty of Medicine Universitas Indonesia CRO.

7.1. Record Retention

Research records for all study subjects including CRFs, laboratory and other investigations data/results are to be maintained by the investigator in secure storage for five (5) years. These records are to be maintained in compliance with all designated IRBs requirements. It is the investigator's responsibility to retain copies of these study records until notified in that they can be destroyed.

6.2 Protocol Deviation

Protocol Deviation is defined as any change, divergence, or departure from the IRB approved study procedures in the research protocol. Protocol deviations are designated as serious or non-serious and further characterized as:

1. *Those that occur because a member of the research team deviates from the protocol.*
2. *Those that are identified before they occur, but cannot be prevented.*
3. *Those that are discovered after they occur*

Serious Protocol Deviation is a deviation that meets the definition of a Serious Adverse Event or compromises the safety, welfare or rights of participants or others.

7.2. Non-Compliance

Non-compliance is defined as the failure to comply with applicable IRB requirements, or regulatory requirements for the protection of human participants. Non-compliance is further characterized as

1. *Serious: Non-compliance that*
 - *Increases risks, or causes harm, to participants*
 - *Decreases potential benefits to participants*
 - *Compromises the integrity of the NIH-HRPP*
 - *Invalidates the study data*
2. *Continuing: Non-compliance that is recurring*
3. *Minor: Non-compliance that, is neither serious nor continuing.*

8. ASSESSMENT OF SAFETY

8.1. Adverse Events

Side effects that can occur in this study are the subjects feels pain at the site of injection for venous blood sample collection, and in some rarely case is a hematoma and dermatitis in the site of injection for venous blood sample.

Patients will be asked about signs and symptoms of atorvastatin toxicity. If any signs or symptoms are reported, patients will undergo clinical and laboratory evaluation to determine if the study drugs need to be stopped.

Stopping criterias:

- ALT level rise above 10-fold upper normal limit or persist in being above 5-fold elevated or are associated with symptoms of liver failure
- Creatine kinase rise 10-fold upper normal limit in patients with clinically rhabdomyolysis
- Severe drug allergic reactions, such as Stevens Johnson syndrome, toxic epidermal necrolysis

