	
10. History of statin hypersensitivity
 
11. Framingham Risk Score above 10% within LDL \geq130
 
12. Framingham Risk Score under 10% within LDL \geq160
 
13. Out of Periodontitis Index (Upper right molars, top series, upper left molars, lower right molars, bottom series, lower left molars)
 
Drop out criteria:
 
 1. Becomes pregnant during this study 2. Stop using ART > 1 month 3. Stop or refuse to continue to use atorvastatin during this study 4. Not willing to continue as participant in this study
Participating sites	HIV Integrated Care Unit, Tertiary Hospital Cipto Mangunkusumo
Study Design	This study using double blind randomized, placebo-controlled clinical trial. Subject chosen by consecutive methods.
Study Scheme or Intervention	Eligible subjects will be randomized to receive an atorvastatin or placebo with a ratio of 1: 1. Atorvastatin 20 mg or identical placebo capsules will be given orally for 48 weeks.
Schedule of Procedures/ Evaluations	
 1. The participants who meet the inclusion and exclusion criterias (except viral load, anti-CMV, and Framingham score criterias) get an explanation of the purpose, method of the study, the rights to stop or refuse to take part during in the study. And each participant gives their sign to ICF. 2. Viral load, IgG anti-CMV, fasted lipid profile, fasting glucose and insuline to define Framingham score will be done as screening process. 3. Participants with CMV seropositivity, undetectable viral load, and Framingham risk score $>$10% LDL $<$130 or Framingham risk score $<$10% LDL $<$160 will continue the study process. 4. Participants will be asked to fast for 10 hours before taking 12 mL of venous blood: for examination of blood glucose, ALT, CMV DNA, and sCD14, VCAM, ICAM, hsCRP, β2M, and transient elastography with CAP. CIMT, FMD, neurocognitive examination, and Community Periodontal Index will be done within a week before taking study drugs. 5. Participants will be randomized to get atorvastatin therapy or placebo. While using study drugs, participants continue their ART and other standard of cares. 6. Study drugs will be dispensed monthly along with ART refill and the pharmacist records the remaining

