	
medication.
 
7. At week 24, blood collection procedures and neurocognitive examination procedures will be repeated.
 
8. At week 48, blood collection procedures, CIMT, FMD, transient elastography with CAP, neurocognitive examination, and community periodontal index procedures will be repeated.

Study Duration	
The study will be conducted from April, 2019 to April, 2021. Predicted accrual period: 4 months Enrollment of the first study participant to enrollment of last participant schedule on four months in the first year.

Primary Endpoint(s)	
The mean or median CIMT changes of virally suppressed HIV patients with CMV seropositivity in atorvastatin group versus placebo group between baseline and week 48

Secondary endpoints	
 - Magnitude of change in effect of atorvastatin on CIMT associated with baseline CMV copy number - The mean or median changes of fasted lipid between baseline and week 24, week 24 and week 48 - The mean or median changes of brachial artery flow mediated vasodilatation (FMD) between baseline and week 48 - The mean or median changes of liver fibrosis and steatosis in atorvastatin and placebo group between baseline and week 48 - The mean or median changes of sCD14, VCAM, ICAM, CRP, and β2M in atorvastatin and placebo group lipid between baseline and week 24, week 24 and week 48 - The mean or median changes of neurocognitive function in atorvastatin and placebo group lipid between baseline and week 24, week 24 and week 48 - The mean or median changes of oral periodontitis score in atorvastatin and placebo group between baseline and week 48 - Magnitude of change in effect of atorvastatin on FMD, neurocognitive function, liver fibrosis and steatosis, lipid profile, and immune activation biomarkers associated with baseline CMV copy number

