4.13.3. Follow Up Visit(s)

Patient will be seen for regular clinical follow up as standard of care in the clinic (monthly/ bimonthly). Follow up visit will include clinical and laboratory procedure as presented in table study schedule (appendix).

At week 24, blood collection procedures and neurocognitive examination procedures will be repeated. At week 48, blood collection procedures, CIMT, FMD, transient elastography with CAP, neurocognitive examination, and community periodontal index procedures will be repeated.

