5.3. Total Blood Volume

Subjects who are willing to take this part in this study will take maximum 12 mL of venous blood sample in each visit (see appendix).

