Fasting blood glucose and insulin		V	V	V	
DPL	V*				
LED	V*				
Store sample					
Serum		V	V	V	
Other Assessment					
Depression assessment	v				

*According to patient's symptom.

Blood volume collection

	Type	Blood collected	screening	randomization	Week 24	Week 48	Extravisit
1 Viral load	Plasma	3 mL	3 mL				
Lipid profile	Serum	2 mL	2 mL		2 mL	2 mL	
Fasting blood glucose	Serum	1 mL	1 mL		1 mL	1 mL	
IgG Anti-CMV	Serum	1 mL	1 mL				
Complete blood count	Plasma EDTA	3 mL		3 mL			
ALT, Creatine	Plasma EDTA	1 mL		1 mL			1 mL
CK	Plasma EDTA	1 mL		1 mL			1 mL
Storage sample	plasma	6 mL	5 mL	6 mL	9 mL	9 mL	
TOTAL volume			12 mL	12 mL	12 mL	12 mL	2 mL

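### Two of the three ALT stopping limits in 8.1 need no symptoms, but the schedule draws no ALT on drug unless a symptom prompts it

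*Combined protocol and SAP*

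**What the plan says.** Section 8.1 gives three ALT grounds for stopping drug: "ALT level rise above 10-fold upper normal limit or persist in being above 5-fold elevated or are associated with symptoms of liver failure". The text just above them says how a participant comes to be tested: "If any signs or symptoms are reported, patients will undergo clinical and laboratory evaluation".

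Section 4.13.3 defines the content of follow-up visits by reference: "Follow up visit will include clinical and laboratory procedure as presented in table study schedule (appendix". In Appendix A the ALT row is marked at randomisation and at the extra visit, and the extra-visit mark carries the footnote "According to patient's symptom". The week 24 and week 48 cells are blank. The blood-volume table gives ALT (with creatinine) 1 mL at randomisation and 1 mL at the extra visit, and nothing at weeks 24 or 48. Section 5.3 caps collection at a "maximum 12 mL of venous blood sample in each visit".

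The synopsis is looser. Step 4 takes baseline blood "for examination of blood glucose, ALT, CMV DNA, and sCD14" and other markers, and step 7 then says: "At week 24, blood collection procedures and neurocognitive examination procedures will be repeated". Step 8 does the same for week 48, and 4.13.3 uses the same wording. None of these sentences names the analytes to be repeated.

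**The concern.** A stopping limit protects participants only if the quantity it acts on is measured. Two of the 8.1 limits are written so that a laboratory value alone can stop the drug, yet the schedule contains no laboratory value on drug for a participant who feels well.

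What is at stake is participant safety. Section 9.2.1 lists severe liver toxicity among the possible serious reactions to atorvastatin. The liver-related exclusions in 4.6.2 are decompensated cirrhosis, acute liver failure and current DAA therapy for hepatitis C. Compensated liver disease, including hepatitis C not under DAA therapy, may therefore enter the trial. ALT is not an endpoint, so the primary comparison of CIMT change does not depend on it.

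**Working it through.** **1. Which limits need symptoms (8.1).**

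| ALT limit | Symptoms required? | Values needed |
|---|---|---|
| Above 10-fold ULN | No | 1 |
| Persistently above 5-fold | No | At least 2 |
| With symptoms of liver failure | Yes | 1 |

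Two of the three can be met by someone without symptoms. The second cannot be judged from a single value, and no section gives an interval for the repeat.

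**2. Where ALT is drawn.**

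| Source | Baseline | Week 24 | Week 48 | Extra visit |
|---|---|---|---|---|
| Appendix A, ALT row | Yes | Blank | Blank | By symptom |
| Blood-volume table, ALT row | 1 mL | Blank | Blank | 1 mL |
| Synopsis steps 4, 7, 8 | Named | Analytes not named | Analytes not named | Not covered |

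Section 4.13.3 refers to the appendix, and both appendix tables agree. The synopsis wording cannot be a literal repeat of the step 4 list, because that list has no lipid profile while lipids are due at weeks 24 and 48. The schedule has to supply the content, and it supplies no ALT.

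**3. Check on the volume table.** Column sums, in mL:

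- Screening: 3 + 2 + 1 + 1 + 5 = 12, as stated.
- Randomisation: 3 + 1 + 1 + 6 = 11 against a stated 12. The 1 mL of glucose that Appendix A marks at that visit would account for the difference.
- Weeks 24 and 48: lipids 2 + glucose 1 + storage 9 = 12 at each visit, as stated.
- Extra visit: 1 + 1 = 2, as stated.

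The week 24 and 48 columns reproduce exactly and already meet the 5.3 maximum. Adding 1 mL for ALT gives 12 + 1 = 13 mL, which exceeds it. As written, the table leaves no room for ALT at those visits. With storage reduced to 8 mL the sum is 2 + 1 + 1 + 8 = 12 mL.

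**4. Which scheduled draw could still change treatment.** Dosing lasts 48 weeks. Week 24 is the only scheduled blood draw at which drug can still be stopped; a week 48 value serves end-of-treatment safety only.

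**5. Cost of adding it.** With 40 participants per arm, 2 × 40 = 80. ALT at week 24 adds at most 80 × 1 = 80 assays, and ALT at both visits adds at most 80 × 2 = 160. Dropout would lower both.

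**The case against.** The strongest reply is that the plan chose symptom-driven monitoring and says so consistently. Section 8.1 introduces the limits through an evaluation triggered by symptoms, 4.13.3 defers to Appendix A, and the two tables match. Section 4.13.4 allows further investigations when clinically indicated, 9.6 lets the researcher discontinue a participant for their well-being, and 4.10 has participants telephoned every two weeks, so symptoms have a fair chance of being reported.

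Most of this stands. A reader might infer that the documents leave it unsettled which ALT values the limits act on. They do not support that: most of the text gives one answer, and the synopsis wording is too unspecific to be a real rival. Appendix A is not a complete list, since it has no FMD row, but every hospital-laboratory test named in 5.2 has a row, so the blank ALT cells carry weight.

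A reader might also infer that the limits were meant to screen the baseline value, or that an entry limit is missing by mistake. The text speaks of a rise and of stopping drug, which describes someone already taking it. An ALT limit for entry would be a new clinical criterion.

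The reply does not meet the remaining point. Clinical discretion and telephone calls cannot act on a symptomless value that nobody has drawn, and two of the limits are written for exactly such a value.

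**Conclusion.** The point holds as a gap between the stopping rule and the schedule. Under the governing schedule, no ALT is measured on drug in a symptom-free participant, so the two limits that need no symptoms can operate only after a symptom has led to a test. The synopsis and 4.13.3 wording about repeating blood procedures is loosely inconsistent with this and should be brought into line.

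The gap covers all 80 planned participants at week 24, but its clinical size is unknown. The documents give no rate of ALT elevation, and a single value above 5-fold would not in any case meet a limit that requires persistence. No probability of a missed stopping event can be derived.

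The conclusion rests on reading Appendix A as the source for follow-up laboratory tests, as 4.13.3 says. If staff in fact draw ALT at weeks 24 and 48 on the strength of the synopsis, the change only records existing practice. This is an inexpensive safety improvement; the sample size, the power and the CIMT conclusion are unaffected.

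**What to change.** - **Appendix A:** mark ALT at week 24. Week 48 is optional, for end-of-treatment safety.
- **Blood-volume table:** at each visit where ALT is added, allot it 1 mL and cut storage from 9 to 8 mL, so that the total stays at 12 mL.
- **Section 8.1:** add that an ALT above 5-fold ULN is repeated no later than the next monthly refill, so that persistence can be judged. Section 4.11.2 already brings participants in monthly, and the extra-visit column already carries 1 mL for ALT.
- **Synopsis steps 7 and 8, and 4.13.3:** refer to the tests marked in Appendix A, so that all places agree.

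The cost is at most 80 more routine hospital-laboratory ALT assays (160 with week 48), 1 mL less stored plasma per participant at each visit concerned, and a repeat ALT for anyone above 5-fold. The number of repeats cannot be estimated from the documents. No visit is added to the routine schedule.

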8.2. Serious Adverse Events

A serious adverse event (SAE) is defined as any adverse event that results in the following

- results in death;
- is life-threatening (places the participant at immediate risk of death from the event as it occurred);

- or based upon appropriate medical judgement, may jeopardize the participant's health and may require medical or surgical intervention to prevent one of the other outcomes listed in this definition.

All SAE will be collected on a specific SAE form and reported to the Faculty of Medicine Universitas Indonesia IRB within a week of occurrence.

The management of AE will be according to best clinical practices at the judgment of the researcher at occurrence.

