4.6.3 Drop Out Criteria

1. Pregnant during this study
2. Stop using ART > 1 month
3. Stop or refuse to use atorvastatin during this study
4. Not willing to continue as participant in this study

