8.4. IRB Reporting

8.5. Expedited Reporting to the NIHRD IRB

Unanticipated Problems, Serious Adverse Events, Serious Deviations, and Serious or Continuing Non-Compliance will be reported within 7 calendar days of investigator awareness to the IRB, regardless of expectedness.

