9.2. Potential Risks and Benefit to the Participant

9.2.1. Potential Risks

Subjects can feel less comfortable and pain in blood sampling. Other complications which may arise are the occurrence of phlebitis (infection in the place of needle puncture) and hematoma (bruising at the place of needle puncture). To reduce discomfort in each subject, blood sampling will be carried out by experienced staff. Furthermore, researchers will guarantee the confidentiality of data from research subjects. The community periodontal index procedures might cause little bleeding.

The possibility of getting side effect related to atorvastatin can also make subject less comfortable. Common reactions include headache, difficulty sleeping, muscle aches, muscle tenderness, or muscle weakness, nausea, vomiting, diarrhea, bloating and constipation. Serious reactions might include severe liver toxicity, tendon rupture, severe allergic reaction and rhabdomyolysis.

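### As extracted, the SAE definition in 8.2 omits hospitalisation, disability and congenital anomaly, so a tendon rupture, which 9.2.1 calls serious, need not be recorded or expedited as an SAE

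*Combined protocol and SAP*

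**What the plan says.** All references are to the combined protocol and SAP.

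Section 8.2 opens with "A serious adverse event (SAE) is defined as any adverse event that results in the following" and then gives three limbs:

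- "results in death";
- "is life-threatening (places the participant at immediate risk of death from the event as it occurred", so the threat must be immediate;
- a medical-judgement limb, for an event that could endanger health and "may require medical or surgical intervention to prevent one of the other outcomes listed in this definition".

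Events that meet this definition go on a dedicated SAE form and are "reported to the Faculty of Medicine Universitas Indonesia IRB within a week of occurrence".

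Section 8.5, whose heading names the NIHRD IRB, covers SAEs, unanticipated problems, serious deviations, and serious or continuing non-compliance. It says these "will be reported within 7 calendar days of investigator awareness to the IRB, regardless of expectedness".

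Section 9.2.1, on risks of atorvastatin, states: "Serious reactions might include severe liver toxicity, tendon rupture, severe allergic reaction and rhabdomyolysis".

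Section 4.6.3 lists "Pregnant during this study" among the reasons for drop-out, so pregnancy on study is foreseen.

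**The concern.** The judgement limb in 8.2 refers back to the other outcomes in its own list. That list holds only death and immediate threat to life, so the limb cannot reach an event whose worst result is an admission, an operation or a lasting disability. The protocol's risk section nevertheless calls tendon rupture serious. Two sections therefore use the same word for different sets of events, and only the narrower set triggers the SAE form and the SAE entry in 8.5.

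At stake is prompt outside notice of harm. Sections 3 and 6.2 name no adverse-event endpoint and no safety analysis, so the classification in section 8 carries most of the weight. Followed to the letter, the trial could report no SAEs although a participant had been admitted with, or disabled by, a drug reaction.

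**Working it through.** No arithmetic applies to the definition. The check sets the sections side by side.

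**1. Events against the limbs of 8.2**

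| Event | Death | Immediate threat to life | Intervention to prevent either | SAE under 8.2? |
|---|---|---|---|---|
| Tendon rupture with surgery, admission or lasting disability, life not at risk | no | no | no | no |
| Admission for muscle or liver toxicity, judged neither life-threatening nor likely to become so | no | no | no | no |
| Rhabdomyolysis, severe liver toxicity or severe allergic reaction, treated to avert a threat to life | no | not necessarily | yes | yes |
| Congenital anomaly after exposure on study, not fatal or life-threatening | no | no | no | no |

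Of the four reactions named in 9.2.1, tendon rupture is the one that clearly falls outside. The other three can qualify before life is actually threatened, because the third limb asks only that intervention may be needed to prevent that.

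**2. Other routes to the IRB**

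- *Unanticipated problem (8.3).* All three conditions must hold, and the first is that the event is unexpected in nature, severity or frequency against the risks described in the study documents. Section 9.2.1 describes these reactions, so they are expected in nature. Only unexpected severity or frequency would bring them in.
- *Annual report (8.6).* Ordinary adverse events are summarised at continuing review, which 9.1 requires at least yearly. Treatment lasts 48 × 7 = 336 days. With yearly review, an event early in treatment could therefore reach the IRB only after that participant had finished.
- *Serious deviation (the Protocol Deviation section between 7.1 and 7.2).* This concerns departures from protocol. A drug reaction under correct conduct is not one.

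**3. Could bullets have been lost in extraction?**

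There is a blank line in 8.2 between the second and third limbs. Similar gaps occur in 3.2 between items 2 and 3, and in the reference list between entries 15 and 16. The numbering there is consecutive, so nothing was lost and a page break is the likely cause. The bullets in 8.2 carry no numbers, so the same test cannot be made there. The reference to other listed outcomes, after only two, would also fit a list that was once longer.

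**4. The reporting rule**

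| | 8.2 | 8.5 |
|---|---|---|
| Period | one week | 7 calendar days |
| Start | occurrence | investigator awareness |
| IRB named | Faculty of Medicine Universitas Indonesia | NIHRD, in the heading only |

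The periods are equal (1 × 7 = 7 days). The start points and the named recipients differ. A clock that starts at occurrence can run out before the site knows of the event.

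**The case against.** The strongest reply is that the gap is narrow. Most severe drug toxicity would come in through the judgement limb, the remaining events are still adverse events that reach the IRB in summary, and the stopping criteria in 8.1 do not depend on SAE status. All of this is right, and it limits the point to recording and expedited reporting. It does not remove the conflict over tendon rupture.

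A second reply is that 9.2.1 is risk wording for participants and was not meant to set a reporting category, and that the conflict by itself supports covering only tendon rupture. This stands in part: not every reaction named in 9.2.1 needs to be an SAE automatically. But an event is described there as serious while 8.2 gives no outcome under which it could be so classed. Hospitalisation and disability are the outcomes by which a non-fatal rupture would be serious. The case for congenital anomaly rests on 4.6.3, which foresees pregnancy.

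Four stronger readings are tempting but not supported:

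- *All four reactions escape unless life is already threatened.* The third limb also covers intervention to prevent that state.
- *The gap passes in full to serious deviations and unanticipated problems.* Each definition has an independent limb: compromised safety, welfare or rights in the one, greater risk of harm in the other. An anomaly in an infant, if possibly related, could be expedited as an unanticipated problem, since 8.3 covers people other than participants and 9.2.1 lists no fetal risk. The consent form is not available, so this cannot be settled.
- *SAE counts by arm would be biased.* No comparison of SAEs between arms is planned.
- *A calculable share of events would miss the clock in 8.2, because retention calls are two-weekly (4.10).* Monthly dispensing, clinic visits and participants' own reports also bring events to light, and the most urgent events need not wait for a call. The documents support no such share.

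On the clock, duties to two IRBs can coexist, so the difference in recipient may be intended. The text does not say.

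**Conclusion.** The point holds: as extracted, 8.2 is too narrow to agree with 9.2.1. Literally applied, it leaves out a tendon rupture that does not threaten life, and an admission for drug toxicity judged neither life-threatening nor likely to become so. The unanticipated-problem route and the annual summary do not reliably make up for this.

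In size, it is a clear omission for one of the four named reactions and a possible one for milder presentations of the other three. How many events this would be among the planned 80 participants (40 per group × 2) cannot be estimated, because the documents give no reaction rates. The sample size and the analysis of CIMT change are unaffected.

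The conclusion assumes that no bullets were lost in extraction and that 8.2 is applied as worded. If the original PDF lists the missing outcomes, the definition point falls away and only the reporting conflict remains. That conflict is separate and smaller, and adds no weight to the definition point.

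**What to change.** First check 8.2 in the original PDF. If the list is as extracted:

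1. Add three outcomes to the SAE definition in 8.2: hospitalisation or its prolongation; persistent or significant disability or incapacity; congenital anomaly or birth defect. The judgement limb then reaches these too, and the definition agrees with the serious reactions in 9.2.1.
2. As a separate edit, needed whatever the PDF shows, bring 8.2 and 8.5 to one reporting clock that starts at investigator awareness, and name the IRB or IRBs that receive the report.

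The cost is a short wording amendment, which 9.1 requires the IRB to approve, and a few more SAE reports on the existing form. No visit, test or analysis changes.
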